3.6 Ancillary Data Collection

In addition to the primary and secondary endpoint analyses, and to the analyses of RF procedure's tolerability parameters, other supplementary data will be collected as part of the study protocol to ensure patient safety and for further examination of the effect of the therapy.

These assessments will include summaries of all adverse events, information obtained during device interrogation (such as time of active RF treatment in each treated site of the soft palate and base of tongue, power in w, and amount of Joules), blood pressure measurements, and other sleep and cardiopulmonary parameters collected during the PSG sleep study. These assessments include, but are not limited to, the variables that follow:

- Lowest Oxygen Saturation during Sleep (LSAT)
- Mean Oxygen Saturation
- Systolic and Diastolic blood pressure changes

All data will be collected on case report forms at each site. Copies will be scanned and sent via email/fax to the sponsor's data coordinators, who will enter the data and visually check for accuracy. The principal investigator at each treatment site will verify data accuracy. Data will be also checked statistically and inconsistencies will be resolved with the raw data at each site.

4 RESEARCH DESIGN

The study is a prospective, single-arm, multicenter study designed to determine the effectiveness of multi-level radiofrequency ablation (RFA) for mild to moderate obstructive sleep apnea. The study aims to recruit a total of 48 patients at 3 study sites. The Medical University of South Carolina Hospital will serve as the primary site with [REDACTED] the PI of the study.

4.1.1 Inclusion Criteria (Subjects)

Patients who meet all of the following criteria may be given consideration for inclusion in this study:

- Adults (≥ 22 years)
- Self-report of daytime somnolence
- Body mass index (BMI) ≤ 32
- Mild to moderate obstructive sleep apnea (AHI 10-30; lowest O₂ sat $\geq 80\%$) OSA based on a prior PSG conducted within 12 months of enrollment, or based on a 2-night home sleep study using the WatchPAT 200S-3.
- Evidence of palate and tongue base collapse on supine fiberoptic examination (Müller's maneuver)
- Have failed or have not tolerated CPAP treatment (See Section 5.1 for definitions)
- Have been offered and are not interested in oral appliance therapy
- No prior surgical treatment for OSAS other than nasal surgery or tonsillectomy.
- Willing and capable of providing informed consent
- Willing and capable to return for all follow-up visits and PSG sleep-studies and filling out the questionnaires.

4.1.2 Exclusion Criteria

Patients who meet any one of the following criteria will be excluded from this study:

- Another significant sleep disorder (e.g., insomnia, periodic limb movement)
- Absence of regular bed-partner
- Tonsillar hypertrophy (3 or 4 plus)
- Chronic Obstructive Pulmonary Disease (COPD)
- Interstitial Lung Disease (ILD)
- Cystic Fibrosis
- Acute Respiratory Distress Syndrome (ARDS)
- Nasal or supraglottic obstruction on fiberoptic examination
- ASA class III, IV, V
- Latex allergy
- Lidocaine allergy
- Pregnancy or plans to become pregnant
Note: women of childbearing potential must demonstrate a negative pregnancy test upon enrollment; those patients qualified to progress to RFA must also demonstrate a negative pregnancy test within 7 days prior to the date of RFA procedure.
- Major depression or non-stabilized psychiatric disorder
- Drug or alcohol abuse
- Previous palatal or tongue surgery
- Stable or unstable angina
- CHF
- moderate or severe valvular disease
- TIA/CVA

- Carotid stenosis or endarterectomy
- Anemia
- Room air SpO₂ < 95%
- Pulmonary hypertension
- Dialysis
- Central or mixed apnea ≥ 10% of respiratory events
- Participation in another clinical study (enrolled in any concurrent study) whose investigational plan is judged to interfere or affect any of the measures of this study

4.2 Sampling Methods

A stratified sample is required to assure patient heterogeneity and representation of the mild and moderate patient in the sample. During recruitment, stratification according to the screening WatchPAT score will take place. Such stratification will be required within all participating medical centers. A list designating number of patients from each stratum will be distributed to the medical centers as part of study set-up. The screening WatchPAT score will serve to estimate AHI results and the patients' stratum prior to recruitment.

For the expected final sample size of n=48 the following stratification

Planned stratified sample scheme:

Strata	AHI level approximated by WatchPAT	Required n (%)
Starta-1	10-15	10 (21%)
Starta-2	15-20	12 (25%)
Starta-3	20-30	26 (54%)

Participating sites are required to meet the specified strata distribution (percentages) as given for the entire sample.

5 PROCEDURES DURING THE STUDY

5.1 Visit 1 - Screening visit and home sleep study

Patient medical records may be initially screened to determine whether an individual meets the general inclusion and exclusion criteria. In addition, the patient must have a history of CPAP failure or intolerance. For the purposes of this study, CPAP failure is identified as an inability to eliminate OSA (AHI remains greater than 10 despite CPAP usage). CPAP intolerance is identified by:

- Inability to use CPAP (device indicates < 5 nights of per week of usage; usage defined as > 4 hours of use per night⁷⁶, as verified by 3-month CPAP smart card data, or
- Unwillingness to use CPAP (e.g., patient returns the CPAP system after attempting to use it⁷⁷).

The nature of CPAP intolerance will be specified in the medical records, reflect adequate attempts to pursue CPAP, and be documented by the study physician in the study database according to one or more of the following reasons.

- Non-compliant and specific reasons for non-compliance including details of CPAP attempts
- Experiencing discomfort because CPAP pressure is too high
- Discomfort due to other reason (specify discomfort)
- Causes undesirable clinical effects (specify undesirable clinical effect)
- Patient not using the system enough (< 4 hours of use per night < 5 nights per week; the CPAP counter number will be documented)
- Patient symptoms persist despite CPAP use

If the patient meets this eligibility criterion, the patient will undergo a 2-night home sleep study using the WatchPAT 200S-3 to determine his/her screened AHI. The patient will be instructed in the use of the device and will return it to the office after the 2-night recording for interpretation. Patients who are qualified on the basis of the WatchPAT sleep study to participate in the study will be presented with the risks, benefits and alternatives to the study and will be asked to enroll in the study.

Patients who meet all eligibility criteria and agree to participate in the study must provide written informed consent that has been approved by the center's IRB. For patients who have a limited proficiency of the country's language, the Sponsor will assist the center in obtaining a written translated consent. Translated consent forms must have IRB approval prior to use.

If the patient does not qualify, the patient will be offered advice by the study physician for further management outside of the study.

5.2 Visit 2- Baseline visit and PSG sleep study

This visit will occur within 2 weeks after the Screening Visit. During the Baseline visit, standard medical history and demographics will be obtained from each patient. Patient descriptive information will include height and weight to calculate the body mass index (BMI), gender, blood pressure, heart rate, race, medications, use of alcohol, snoring history, effective CPAP pressure, and the information gained from the study' questionnaires ((Epworth Sleepiness Scale (ESS) and Functional Outcomes of Sleep Questionnaire (FOSQ)).

In addition, the patient will undergo a Müller's Manoeuvre^{37, 38}, a technique that looks for collapsed sections of the upper airways such as the oropharynx and hypopharynx. In this maneuver, a fiberoptic scope is passed into the upper airway through the nares while the patient is in supine position. The patient attempts to inhale with mouth closed and nostrils plugged. This leads to a collapse of the airway which can be directly observed with the fiberoptic scope. Müller's maneuver is used to help determine the site of airway obstruction. A positive test result means observation of obstruction at either the retropalatal airway (soft palate; tonsils; lateral pharyngeal walls), retrolingual airway (base of tongue), or a combination of the two sites. Patients will be classified according to the method of Fugita⁷⁵ as Class I if only retropalatal collapse is present; class II if both retropalatal and retrolingual collapse is present; and class III if only retrolingual collapse is observed.

Laboratory polysomnography (PSG) will be done no later than 90 days after enrollment and prior to first treatment. PSG will be conducted using standard techniques in the sleep laboratory. The AASM Manual of Scoring Sleep, 2007 will be used as a guideline for rules⁷⁸, terminology and technical specifications for the PSG study in all study centers. Briefly, the following list of recordings will be collected:

1. Three channels of electroencephalogram
2. Chin electromyogram
3. Two channels of electrooculogram
4. A single bipolar modified Lead II for electrocardiogram
5. Chest and abdomen belts for respiratory effort measurement
6. One oronasal thermal sensor to detect the absence of airflow for apnea
7. One nasal pressure transducer for detection of airflow for hypopnea
8. One finger oximeter to continuously monitor arterial oxygen saturation
9. One position sensor to electronically determine position (supine, left, right, prone), or a means for documenting position
10. One leg electromyogram to record leg movements

All signals will be recorded on a digital PSG system and stored for off-line analysis by the PSG core lab.

Prior to the PSG, the patients will fill out, or respond to, a Pre-PSG Interview that contains questions about recent behavior that may affect sleep during the PSG.

During the PSG, the coordinator or PSG technician will fill out a PSG Log indicating technical aspects of the PSG recording that the Core Lab needs to score the PSG file, such as signal montage filtering and user events including body positions. The user events and body positions may be recorded directly onto the PSG recording system rather than on the PSG log if the recording system can create a readable file of the user notes that a core lab can use to assist with scoring.

Subjects who fail to show mild-to-moderate OSA (AHI 10-30; Lowest O2 sat. > 80%) on the baseline PSG will not proceed to treatment and will be considered a screening failure. These subjects will be offered alternative therapy by their study doctor as indicated.

5.3 Visit 3- Stage I: First Radiofrequency Treatment (within 4 weeks of baseline PSG)

The research team will greet the patient and will escort him to triage for vitals. The patient will then be escorted to the procedure room, and will be given oral antibiotics prior to the treatment. The patient will be asked to complete the specified questionnaires and VAS scales concerning, snoring (bed partner), speech and swallowing in order to capture patient's baseline perceived pain and level of speech and swallowing function. VAS for pain will be conducted at the end of this session. The patient will be sitting upright in an examination chair. A crash cart is available in all units where the procedure is performed. Surgeons have both BLS and/or ACLS training. The patient will then undergo the first of three radiofrequency treatments to the upper airway. Radiofrequency ablation procedures will take

place in an outpatient setting under local anesthesia. The RFA procedure will be performed using standard surgical techniques and a new RFA applicator will be used for each of the 3 treatment visits. To perform RFA of the soft palate, a tongue blade will be inserted, bringing the palate into view. The soft palate will be anesthetized with three sprays of topical anesthetic using a typical spray applicator (benzocaine 14%, butamben 2.0%, tetracaine hydrochloride 2.0%; Cetacaine®) followed by an injection of 8 to 10 cc of 1% lidocaine with 1:100,000 epinephrine. The physician will then insert the surgical handpiece needle electrode into the submucosal tissue of the soft palate. The radiofrequency generator delivers energy beneath the surface tissue while monitoring temperature. Tissue is heated in a limited area around the needle electrode, creating a coagulative lesion beneath the surface. The energy application is immediately aborted if there are signs of tissue blanching on the mucosal surface. Discomfort is minimal during the procedure and the surface tissue is protected from thermal damage by the submucosal lidocaine infiltrate which expands the thickness of the soft palate tissue. A single-prong RFA applicator (CelonProSleep *plus*, Olympus, Germany) is used to create 7 lesions of 54 joules (J) each (Celon Power Setting 12W, as indicated in the Instruction for Use): two laterally above the anterior tonsillar pillar; two paramedian to the uvula; and three at the hard and soft palate junction (Fig. 1).

Following the procedure, the patient rinses his/her mouth with cool tap water. The throat is checked in 5 minutes by the surgeon to make sure there is no ongoing oozing. In the event of ongoing ooze, the spot will be treated with a stick of silver nitrate cautery.

[figure not shown]

Fig. 1 Points of RF treatment – soft palate

The 7 lesions in the documented positions provide sufficient energy application to the soft palate without concern of extensive energy overlap. A 54 J lesion creates an average lesion size of 0.40 cubic centimeters, and each lesion is a centimeter or more removed from the adjacent lesion. The probe is placed in the submucosal tissues so that the probe cannot be seen through the overlying mucosa. The physician will perform a gentle tug on the probe once inserted to make sure that it is in the proper position within the palatal muscles and not within the submucosal tissues. The natural contour of the probe prevents penetration through the soft palate, and the generator will fail to activate if the tip of the probe is not within tissue.

To perform RFA of the tongue base, the anterior tongue is grasped by the surgeon with clean gauze. The tongue is sprayed with 3 sprays of topical anesthetic (benzocaine 14%, butamben 2.0%, tetracaine hydrochloride 2.0%; Cetacaine®) followed by an injection of 6 cc of 1% lidocaine with 1:100,000 epinephrine in the middle third of the tongue posterior to the circumvallate papillae. The patient then undergoes 6 lesions of RFA each placed 1cm from the midline for a total of three lesions on either side of the tongue. The tongue base is the posterior 1/3 of tongue posterior to the anterior tonsillar pillars and circumvallate papilla. The area to be treated corresponds to the middle third of the tongue base which includes the highest dorsum of the tongue and 1 centimeter to either side of the midline (Fig. 2). The CelonProSleep *plus* single prong applicator will then be used to create the 6 lesions spaced approximately 1 cm apart of 80-84 J each (Celon Power Setting 7W, as indicated in the Instruction for Use). As higher power settings lead to smaller lesion sizes, the recommended power settings for soft palate and base of tongue were chosen to fit into the body structure without endangering the mucosa if the lesion becomes too big.

After the RF treatment, the patient then rinses his/her mouth with cool tap water. The throat is checked in 5 minutes by the surgeon to make sure there is no ongoing oozing. In the event of ongoing ooze, the spot will be treated with a stick of silver nitrate cautery.

[figure not shown]

Fig 2 Points of RF treatment – Base of tongue

After completion of both RFA procedures, the research team will monitor the patient for up to 3 hours post-procedure. Patients must demonstrate adequate pain control, breathing, swallowing and speech prior to discharge. The patient's vitals will be taken prior to the patient being released from the clinic. The research team will ask the patient to walk around the clinic for five minutes to assess the patient's post-operative status. The patient will be provided prescriptions for an antibiotic (amoxicillin or clindamycin), an oral steroid (7-day methylprednisolone taper pack), and an oral pain medication to take if needed (Acetaminophen/Hydrocodone). In addition, the patients will be asked to have a soft diet for at least 2 days after the RFA treatment. The patient will then repeat the questionnaires specified above. Patients will be asked in advance to have their bed partner present to drive them home. The research team will escort the patient and bed partner out to the car. Each patient will be provided an emergency contact number to allow them to contact study personnel or their designees 24-hours a day. The patients will repeat the pain, speech, and swallowing VAS scales at 1, 3, and 7 days post RFA treatment via telephone in order to document persistent ongoing pain, and post-treatment discomfort. The number of pills of narcotic pain medication (hydrocodone-acetaminophen 5mg/325mg; Maximum 2 tablets every 6 hours, or 8 tablets per day; Narco®) used in the first 7 days following the procedure will be recorded.

Clinical examination and assessment of the palate and base of tongue will be performed at days three and 10 following each RF procedure to observe effects on speech and swallowing, as well as other complications as described in the Table below.

Following medical actions will be taken in case of development of side effects and/or complications due to the RFA treatment: Minor and moderate complications such as mucosal ulceration, mucosal crusting, uvular sloughing, hemorrhage controllable in clinic, palatal edema, mild dysphagia, and local infection can be managed with antibiotics, topical medicated gargles, and regular follow-up until the events resolved. Severe complications such as tongue abscess or airway distress due to edema may require hospitalization for medical care (IV fluids; steroid; antibiotics) and/or surgical intervention (airway support; abscess drainage). In a case of an emergency situation arise in the office each treatment center should be fully equipped with crash cart and should have access to a full array of endoscopic and surgical instruments. Rapid transport to an Emergency Department should be available should the need arise.

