3.3 Secondary Efficacy Endpoints

To determine whether multi-level radiofrequency ablation of the upper airway in adults with OSAS with the CelonProSleep *plus* bipolar electrode improves daytime sleepiness, snoring, percentage sleep

time at $\text{SaO}_2 < 90\%$, and sleep-related quality of life without a significant increase in pain, speech or swallowing dysfunction.

The following tools will be applied in order to determine the secondary aims: (1) Epworth Sleepiness Scale (ESS); (2) Functional Outcomes of Sleep Questionnaire (FOSQ), (3) SaO_2 , and (4) 100 mm VAS scale concerning snoring. ESS, FOSQ, and $\text{VAS}_{\text{snoring}}$ will be assessed at Baseline, 6 weeks after completion of each upper airway RF ablation treatments, and 6 months post-treatment. The percentage sleep time with $\text{SaO}_2 < 90\%$ will be determined at the final 6-month PSG.

Secondary endpoint statistical analysis includes descriptive statistics of percentages, Means and SD; In cases in which inference will be added to the value, it will be then corrected with Holm's adjustment for testing multiplicity.

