3.5 Safety and tolerability of RFA Treatment

Safety of radiofrequency treatment will be assessed via the description of all reported adverse events. Adverse events will be summarized by seriousness, severity, relatedness to the procedure and temporal relationship to the procedure. Acute adverse events are those within 14 days of each radiofrequency treatment, long-term adverse events are those events occurring from two weeks following the final treatment until the final 6-month follow-up. No formal statistical hypotheses will be tested.

RFA specific adverse events and complications will be defined as follows (modified after Kezirian et al., 2005)⁴⁵:

- Minor: mucosal ulceration, mucosal crusting, or uvular sloughing,

- Moderate: hemorrhage that is controllable at the office, nerve paresis, or dysphagia to solid food,
- Severe: palatal fistula, hemorrhage requiring hospitalization, nerve paralysis, dysphasia requiring tube feeding, and serious infection or airway compromise requiring hospitalization or surgical intervention.

Tolerability of RFA treatment will be determined with various 100 mm VAS scales concerning pain, speech, and swallowing in order to capture patients' perceived pain, and level of speech and swallowing functions after each RFA treatment. The VAS scales will be scored by the patient immediately following each RFA procedure and 1, 3 and 7 days post-procedure. The use and amount of narcotic pain medication (hydrocodone-acetaminophen 5mg/325mg; Maximum 2 tablets every 6 hours, or 8 tablets per day; Narco®) by pill count will be recorded after each treatment. Mean score and the 95% confidence interval for the tolerability VAS scales at each RFA visit will be calculated to capture tolerability profile.

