6 DURATION

This study has a minimum of eight visits. The first visit, the Screening Visit, is planned for determining whether patient qualifies for the study. This visit will take up to 1 hour. In the second visit, the Baseline Visit, which occurs up to 2 weeks later, standard medical history, demographics and various questionnaires will be obtained from the patient. In addition, the patient will undergo a Müller's Maneuver and will be sent to the sleep lab for a PSG study (one night). This visit will last about 60 minutes.

The third visit is the first RF treatment session and will last about 1 hour. The fourth and fifth visits involve additional RF treatments and will last about one hour each. The first follow-up visit will occur 6 weeks after the third treatment visit and will last as well about 1 hour. The 7th visit, the 6-month follow-up visit, will occur 6 months later and will be no more than 1 hour. At the end of this visit the patient will be admitted to a sleep labor for undergoing the 2nd PSG study. Finally, the 8th and final Visit will last about 30 minutes. The patients may require additional visits in case of complications that are needed to be treated in the hospital or if they have a question or concern. The entire duration of the study for an individual patient is no longer than 24 weeks plus 6 months of follow-up.

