4. Functional Outcomes of Sleep Questionnaire (FOSQ) - The FOSQ is a quality-of-life questionnaire designed specifically to evaluate the impact of disorders of excessive sleepiness on activities of daily living. This is a self-report measure that assesses the effect of excessive sleepiness on activities of ordinary living, including activity level, vigilance, intimacy and sexual relationships, general productivity, and social outcomes. The patient will complete a FOSQ at the Baseline, at Visit 3 (prior to the 1st RFA treatment), Visit 4 (prior to the 2nd RFA treatment), at Visit 5 (prior to the 3rd RFA treatment), at Visit 6 (6-Weeks follow-up post 3rd RFA treatment), and at Visit 7 (6-months follow-up).

5. Pain will be measured on a 10-point Visual analog Scale (VAS_{PAIN}, 0 = "no pain" and 10 = "severe pain"). Measurements will be done on day 1, 3, and 7 post (each) RFA treatment.

6. Snoring will be measured on a 10-point Visual analog Scale (VAS_{SNORING}) and filled out by the bed partner. This scale will be used to assess by the patient and his/her bed partner snoring levels. The scale will range from 0 (no snoring noise) to 10 (extreme noise - bed partner leaves the room). Measurements will be done on day 1, 3, and 7 after the first RFA treatment, on the 2nd and 3rd RF treatments, prior to the treatment and on both follow-up visits.

7. Functional parameters such as speech and swallowing will be measured on a 10-point Visual analog Scale (VAS_{SPEECH} / VAS_{SWALLOWING}) ranging from zero (no problems/not affected) to 10 (severe problems/severely affected). Measurements will be done on day 1, 3, and 7 post each RFA treatment.

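### No pain score is scheduled before the first RFA, so change in pain from the pre-treatment level cannot be calculated for any patient

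*Combined protocol and SAP*

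**What the plan says.** Section 3.3 states the secondary aim as improvement in sleepiness, snoring, oxygen saturation and quality of life "without a significant increase in pain, speech or swallowing dysfunction".

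Section 5.3 (Visit 3, first RFA) has the patient complete questionnaires and VAS scales on snoring, speech and swallowing before treatment, "in order to capture patient's baseline perceived pain and level of speech and swallowing function". The following sentence is "VAS for pain will be conducted at the end of this session".

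Section 3.5 treats pain, speech and swallowing as tolerability measures: "The VAS scales will be scored by the patient immediately following each RFA procedure and 1, 3 and 7 days post-procedure". The analysis it plans is a mean score with 95% confidence interval at each RFA visit, and it says that no formal hypotheses will be tested.

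Section 7, item 5, on the pain VAS: "Measurements will be done on day 1, 3, and 7 post (each) RFA treatment". Sections 5.6 and 5.7 add a pain VAS at Visits 6 and 7.

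**The concern.** An increase is a difference between two values. The study has one arm, so the only valid reference for pain after treatment is the same patient's pain before treatment. Section 5.3 recognises this by naming baseline pain as something to capture, and then leaves pain off the list of scales done beforehand.

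At stake is the pain clause of the aim in section 3.3. If a patient reports some pain at Visit 6 or 7, the data cannot show whether it is new, unchanged or less than before. The value cannot be recovered later, because every subsequent pain score, including any before the second or third RFA, follows at least one ablation.

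**Working it through.** No figure in the plan depends on this point, so there is none to reproduce. The check is to go through every place that gives a time for the pain VAS.

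| Place | Pain VAS before first RFA? | Pain VAS afterwards |
|---|---|---|
| 5.2, Visit 2 (Baseline) | No; the questionnaires named are ESS and FOSQ | – |
| 5.3, Visit 3 | Named as a purpose, absent from the list of scales | End of session; days 1, 3 and 7 |
| 3.5 | No | Immediately after each RFA; days 1, 3 and 7 |
| 5.4 and 5.5, Visits 4 and 5 | – | Days 1, 3 and 7 |
| 5.6 and 5.7, Visits 6 and 7 | – | At the visit |
| 7, item 5 | No | Days 1, 3 and 7 after each RFA |
| Appendix I | No mark at Visit 1 or 2 | Visits 3 to 5 marked for days 1, 3 and 7 after treatment; Visits 6 and 7 |

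In Appendix I the physical-examination row names the day of RF treatment as well as later days. The pain row gives only the days after treatment.

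**Meaning of the session.** Section 6 says: "The third visit is the first RF treatment session and will last about 1 hour". Section 3.5 puts the first score immediately after the procedure. The end of the session is therefore after the ablation.

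**Count.** Scheduled pain scores before the first RFA: 0. Patients with a calculable change from the pre-treatment level: 0 of up to 48.

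**What can still be learned.** Section 7 anchors the pain scale at 0 (no pain) and 10 (severe pain). For one patient let the change be d = post − pre.
- Since pre ≥ 0, d ≤ post.
- Since pre ≤ 10, d ≥ post − 10.
- Averaging over the patients scored at a visit: (mean post − 10) ≤ mean change ≤ mean post.

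A low mean with a tight interval would rule out a large increase. A high mean would be uninterpretable as a change. The lower bound is too wide to be of use.

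**What the missing score would give.** The documents give no SD for change in pain, so precision is shown in SD units. The 95% half-width for a paired mean change is about 1.96/√n:
- n = 43: 1.96/6.557 = 0.30 SD
- n = 48: 1.96/6.928 = 0.28 SD

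**Speech and swallowing.** Section 5.3 does place these scores before the first RFA, but sections 3.5 and 7 (item 7) and Appendix I do not list them. The schedule for those two scales also disagrees with itself.

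**The case against.** The best defence is section 3.5. It is the section that plans an analysis of the pain VAS, and what it plans is descriptive: means and intervals at each RFA visit, with no change from baseline and no test. Section 3.3 lists four tools for the secondary aims (ESS, FOSQ, SaO₂ and the snoring VAS), and pain is not among them. Section 3.4 states no pain hypothesis. So no analysis specified for pain fails. This stands, and it limits the weight of the point. It does not remove it: section 3.3 still speaks of an increase, section 5.3 still promises a baseline, and even a descriptive change needs one.

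A second defence is that the session could mean the questionnaire session, since seating and treatment are described after that sentence. Sections 3.5 and 6 and Appendix I favor the later time. If sites could read it either way, some might collect a baseline and others not, so the text needs correcting in any case.

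A third is that pain before treatment is probably near zero. The documents do not say so.

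Two stronger inferences are tempting, and the documents do not support them:
- A reader might infer that pain cannot be assessed at all. Its level and course from the end of each session to six months can be described, pill counts of narcotic pain medication add to that, and the scores bound any increase from above.
- A reader might infer that change will be biased because the end-of-session score, taken after ablation and local anesthetic, will serve as baseline. It would be a poor baseline, but no analysis section proposes to use it as one.

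**Conclusion.** The point holds as a gap between the stated aim and the assessment schedule, and as a contradiction within section 5.3. Change in pain from the pre-treatment level cannot be calculated for any patient. Post-treatment levels can be described as section 3.5 intends, and they limit the increase only from above.

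The conclusion rests on reading the session in section 5.3 as the treatment session, which sections 3.5 and 6 support, and on there being no pain score on a form outside these documents. The upper bound needs only that the scale cannot go below 0.

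The primary responder endpoint, the four listed secondary endpoints and the sample size are unaffected. The change is worth making because it is nearly free and the missing value cannot be obtained once a patient has had the first RFA.

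**What to change.** 1. Section 5.3: add the pain VAS to the speech and swallowing VAS completed before the first RFA at Visit 3, and keep the end-of-session pain score as a separate post-procedure measurement.
2. Section 3.5, section 7 (items 5 and 7) and Appendix I: list the pre-RFA scores for pain, speech and swallowing, so that all places give the same times.
3. Section 3.5: add a descriptive change from the pre-RFA score, as mean and 95% confidence interval, at days 1, 3 and 7 and at Visits 6 and 7. No formal test is needed.

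For any patient treated before the amendment, report pain levels only and do not impute a baseline of zero. If the score is not added, section 3.3 should be reworded to describe pain after treatment rather than an increase in it.

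The cost is one more VAS line at a visit where similar scales are already completed, plus edits to three sections and the flow chart. There is no extra visit and no change to the sample size.
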